1 TITLE

The BALANCED Anaesthesia Study. A prospective, randomised clinical trial of two levels of anaesthetic depth on patient outcome after major surgery

2 RATIONALE

Current public perceptions are that anaesthesia is very safe and indeed in healthy patients mortality purely attributable to anaesthesia is ~1:200,000 anaesthetics. However the influence of anaesthetic technique on perioperative outcome has barely been explored. Where such trials have been performed, they have also not shown the expected results. The MASTER trial, conducted in Australia and New Zealand in the 1990's comparing major regional anaesthesia for post-operative pain relief with intravenous analgesics showed no difference in mortality in spite of strong evidence from meta-analysis. The POISE trial, a major international trial with strong Australian and New Zealand input on the role of beta-blockade in preventing myocardial infarction and death in patients with ischaemic heart disease also showed increased mortality. This was due to an unexpected increase in strokes counterbalancing the expected decrease in myocardial infarctions. These results have led to a call for more outcome studies to answer important public health questions about how we conduct anaesthesia.

3 STUDY DESIGN AND OBJECTIVES

3.1 Design

International multicentre, prospective, randomised, double blind (subjects, investigators and outcomes assessors), active control, parallel assessment, intention to treat, safety and efficacy study comparing bispectral index (BIS) target groups 50 and 35.

3.2 Primary Objective

The primary efficacy objective is to compare one-year all-cause mortality between the randomised BIS target groups 50 and 35.

3.3 Secondary Objectives

The secondary efficacy objective is:

- To compare secondary efficacy/safety endpoints to one-year between randomised BIS target groups 50 and 35.

The secondary endpoints are:

1. **MI:** According to the 3rd Universal Definition (Thygesen K, Alpert JS, Jaffe AS, et al. Third universal definition of myocardial infarction. Circulation 2012;126:2020-35.), defined by either of:
 - A typical rise of troponin OR a typical fall of an elevated troponin OR a rapid rise and fall of CK-MB, PLUS one of the following: i) ischaemic symptoms, ii) pathological Q waves, iii) ECG changes indicative of ischaemia, iv) coronary artery intervention, and/or v) new or presumed new wall motion abnormality on echo or mibi scan; OR
 - Autopsy findings of MI
2. **Cardiac arrest:** Defined as a successful resuscitation from either documented or presumed ventricular fibrillation or sustained ventricular tachycardia or asystole
3. **Pulmonary embolism:** high probability VQ scan or documented on pulmonary angiogram or spiral CT, or at autopsy
4. **Stroke:** cerebral infarction or haemorrhage on CT or MRI scan, or new neurological signs (paralysis, weakness or speech difficulties) lasting more than 24 hours or leading to earlier death
5. **Sepsis:** using Centers for Disease Control and Prevention with National Healthcare Safety Network criteria: - SIRS plus infection (positive blood culture or purulence from any site)
6. **Surgical site infection:** if associated with purulent discharge and/or a positive microbial culture
7. **MI, cardiac arrest, PE and stroke:** the composite of secondary cardiac endpoints 1 to 4.
8. **Total ICU stay:** including initial ICU admission and readmission time
9. **Hospital stay:** from the start (date, time) of surgery until actual hospital discharge.

10. **Awareness:** Questioning for evidence of awareness under anaesthetic using the modified Brice questionnaire administered once in hospital, preferably on the day following surgery, and again on day 30.
11. **WHODAS score:** pre-operative, day 30 and 1 year
12. **Disability free survival:** disability-free survival up to 1 year: survival and freedom from new-onset disability, the latter defined as a 4-point or greater increase in the WHODAS score. Disability will be assessed by the participant, but if unable then we will use the proxy's report. The date of onset of new disability will be recorded.
13. **Persistent post-operative pain:** pain over the surgical site, for at least three months after surgery, that cannot be explained by other causes, such as disease recurrence or a pre-existing pain syndrome
14. **Cancer recurrence:** defined as clinical radiological or pathological evidence for recurrence of the tumour either at the local or a distant site.
15. **Adverse Events:** all adverse events collected during the study categorised by preferred term.

3.4 Exploratory Objectives

1. **Infection composite:** the composite of secondary endpoints 5 and 6 (sepsis, surgical site infection).
2. **Composite of mortality and cardiac events:** the composite of the primary endpoint (mortality) and MI, cardiac arrest, PE and stroke.

4 GENERAL ANALYSIS DEFINITIONS

4.1 Treatment Allocation

Once all entry details are recorded and eligibility confirmed, randomisation will be performed by contacting the automated on-line randomisation service with back-up phone service. Assignment to one of the two groups will be stratified by collaborating centre-group and a unique study number assigned.

4.2 Sample size calculation

One year all-cause mortality is expected to be ~10% based on the findings of Leslie et al. and Gurman et al. The relative risk reduction in mortality in the BIS=50 group is expected to be 20%. A power analysis using $p_1=0.10$ and $p_2=0.08$ indicates that $N=3250$ patients are required in each group, $1-\beta=0.8$, $\alpha=0.049$. The alpha level is reduced to allow for the single interim analysis.

4.3 Participant Populations

4.3.1 Intention-To-Treat Population (ITT)

The primary and secondary outcomes will initially be analysed using the full analysis set population i.e. the intention-to-treat population which includes all randomised patients undergoing induction of general anaesthesia for surgery. Sensitivity analyses will also be undertaken, as appropriate. In these analyses missing outcome data will be assigned a poor outcome.

In the event that patients withdraw (discontinue participation in the study or are lost to follow-up), information on their survival and secondary endpoint status at the time they are withdrawn will be included in the relevant endpoint analysis.

4.3.2 Per-Protocol (PP) Population

The per-protocol (PP) population will be defined as all randomised participants classified according to the actual median BIS value achieved irrespective of randomisation. Participants will be allocated to the BIS=50 group if the achieved median BIS is between 45 and 55 inclusive, and to the BIS=35 group if the achieved median BIS is between 30 and 40 inclusive. Participants who are not within these ranges will be excluded from these analyses. All primary and secondary endpoints will be compared between the two groups defined as per-protocol. In the event that patients withdraw (discontinue participation in the study or are lost to follow-up), information on their survival and secondary endpoint status at the time they are withdrawn will be included in the relevant endpoint analysis.

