7.2 Physiological data

Bispectral index (BIS), mean arterial pressure (MAP) and minimum alveolar concentration (MAC) of the volatile anaesthetic agent for each patient during anaesthesia will be recorded digitally whenever possible. Analysis will be from first BIS<50 after commencing anaesthesia or 5 minutes after anaesthesia induction if BIS<50 not achieved in that time period, until switch-off of volatile anaesthetic at the end of the case. Mac will not be adjusted for age.

BIS recordings will be visually inspected, obvious artefacts removed and then cleaned by removing all data when the signal quality index is less than 50%, when signal quality is available. Mean BIS for each individual patient will then be calculated.

Mean MAC during this time period will also be calculated for each patient.

Mean MAP will be calculated for each patient during this time period. In addition mean of the target MAP range will be calculated. Mean $(MAP - MAP_{target})$ will then be calculated to establish how well the patient has tracked.

These values will be reported in the ITT summaries as mean and standard deviation for each group

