9.1 Additional analyses

- Additional analyses of efficacy endpoints will be undertaken using the PP participant population and including the intermediate BIS group 40 to 45.
- Efficacy endpoints will be summarised by randomized group within categories for age, ASA, surgery type, centre, use of vasopressors/inotropes and anesthetic duration (quartiles). These results will be summarized using forest plots and the consistency of the difference between randomised groups tested using interaction terms within Cox-regression and general linear models as appropriate.
- Multi-variate analyses will be used to explore the independent and combined effects of randomised treatment, age, ASA, surgery type, study centre-groups, anesthetic duration, the use of inotropes, achieved MAP and achieved BIS group on the efficacy endpoints.

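### The 'per-protocol' analysis regroups patients by achieved BIS whatever their randomised arm, so it is an as-treated comparison that needs relabelling and its own baseline adjustment

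*Combined protocol and SAP*

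**What the plan says.** Section 4.3.2 forms the per-protocol population from "all randomised participants classified according to the actual median BIS value achieved irrespective of randomisation". The rule for the lighter group is: "Participants will be allocated to the BIS=50 group if the achieved median BIS is between 45 and 55 inclusive". The deeper group follows the same pattern, with patients assigned "to the BIS=35 group if the achieved median BIS is between 30 and 40 inclusive". Anyone else is dropped: "Participants who are not within these ranges will be excluded from these analyses". The scope is wide: "All primary and secondary endpoints will be compared between the two groups defined as per-protocol". The section states no covariate adjustment and no limit on interpretation.

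Other sections bear on this:

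- Section 8.1 makes the primary test an intention-to-treat comparison, grouped as randomised.
- Section 9.1 lists the per-protocol work under additional analyses, "using the PP participant population and including the intermediate BIS group 40 to 45". It separately plans exploratory multivariable models that contain achieved BIS group along with randomised treatment, age, ASA, surgery type, centre group, anaesthetic duration, inotrope use and achieved MAP.
- Section 5 provides for adjustment in sensitivity analyses if baseline imbalances appear between randomised groups.
- Section 7.2, on the physiological recordings, says: "Mean BIS for each individual patient will then be calculated". It does not mention a median.

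**The concern.** A per-protocol set normally keeps adherent patients in the arm they were assigned to. Here the assigned arm plays no part: crossovers are moved to the opposite group rather than excluded. Achieved BIS may depend on the patient's condition as well as on the target, and condition also drives one-year death. Grouping on achieved BIS therefore brings back the confounding that randomisation removes. The SAP recognises a related hazard in section 9, where it says that hypotension accompanying deep anaesthesia may explain the mortality difference in earlier evidence.

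At stake is the reading of a table that covers mortality and every secondary endpoint. If it differs from the intention-to-treat result, the label invites readers to take it as the effect in patients who followed the protocol, when part or all of the difference could come from who ended up in each band.

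**Working it through.** **1. The plan's own figure.** Section 4.2 uses 10% vs 8%: "The relative risk reduction in mortality in the BIS=50 group is expected to be 20" per cent, a risk ratio of 0.08/0.10 = 0.80. With two-sided alpha 0.049 (z = 1.969) and power 0.80 (z = 0.842),

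n = [1.969·√(2·0.09·0.91) + 0.842·√(0.10·0.90 + 0.08·0.92)]² / 0.02² = 3233 per group,

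which is 0.5% below the stated 3250. The figure reproduces, and 0.80 is the yardstick below.

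**2. A case that can be checked by hand.** Assume no depth effect, overall mortality 9% (the midpoint of 10% and 8%), 20% of patients frail, and three times the mortality in the frail. Robust mortality is 0.09/(0.8 + 0.2·3) = 0.0643. Let 30% of frail BIS=50 patients fall into 30–40, 30% of robust BIS=35 patients rise into 45–55, and 5% of everyone else cross. Per unit of each arm:

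- Achieved 30–40: frail 0.2·0.95 + 0.2·0.30 = 0.25; robust 0.8·0.70 + 0.8·0.05 = 0.60. Frail share 0.25/0.85 = 0.294; mortality 0.0643·(1 + 2·0.294) = 10.2%.
- Achieved 45–55: frail 0.2·0.70 + 0.2·0.05 = 0.15; robust 0.8·0.95 + 0.8·0.30 = 1.00. Frail share 0.15/1.15 = 0.130; mortality 0.0643·(1 + 2·0.130) = 8.1%.

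The spurious ratio is 0.79. Replacing 30% by 20% gives 0.87, and by 10% gives 0.955. As randomised, the ratio is 1.00.

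**3. A graded model.** Let z be standard Normal frailty. Death: logit P = a + 0.8z, with a set to give 9% overall. Achieved median BIS: arm mean − s·z + Normal error, SD 5. No depth effect. Patients are grouped by 45–55 and 30–40. None of these inputs is in the documents. Mortality ratio, 50 vs 35:

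| Arm means | Grouping | s = 1 | s = 2 | s = 3 |
|---|---|---|---|---|
| 50 and 35 | achieved band (SAP) | 0.98 | 0.95 | 0.90 |
| 50 and 35 | own randomised band | 1.00 | 1.00 | 1.00 |
| 47.5 and 38.5 | achieved band (SAP) | 0.85 | 0.73 | 0.64 |
| 47.5 and 38.5 | own randomised band | 0.89 | 0.81 | 0.75 |

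Sensitivity of the SAP grouping in the converging case:

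- Frailty log-odds ratio 0.4 instead of 0.8: 0.92, 0.85, 0.80.
- SD 5 taken as the total spread of BIS, frailty included: 0.85, 0.72, 0.61.
- Frail patients running 2 points per SD higher: 1.37.

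**4. How much is due to the regrouping.** In the converging case with s = 2, ln 0.81 / ln 0.73 = 0.211/0.315 = 0.67. About two-thirds of the log-scale bias remains when patients stay in their own arm, because selecting on achieved BIS is itself selective. On target, the own-band set removes all of it.

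**5. Share of crossovers** (ignoring frailty, SD 5). On target, an own-band patient has probability Φ(1) − Φ(−1) = 0.683 and a crossover Φ(−2) − Φ(−4) = 0.023, so crossovers are 0.023/0.706 = 3% of those classified. For arms at 47.5 and 38.5, the averages over arms are (0.625 + 0.573)/2 = 0.599 and (0.067 + 0.096)/2 = 0.082, so crossovers are 0.082/0.681 = 12%.

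**The case against.** The other side has a good case on consequence. The primary test is intention-to-treat. Section 4.3.1 takes that population first for the secondary outcomes too. The 0.049 threshold in section 8.1 and the Holm procedure in section 8.2.1 name no per-protocol test. The grouping rule is stated openly, and section 7.1 describes associations with achieved BIS as exploratory. All of this stands, and it limits the severity.

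It can also be said that section 9.1 already plans adjusted models with achieved BIS group. So a reader who infers that the plan contains no adjusted analysis of achieved depth would be wrong. But those models are not tied to the per-protocol comparison, and they omit Charlson score, cancer and emergency status, all of which section 5 lists among the baseline variables.

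A reader might infer that the per-protocol table will show a ratio near 0.80. The documents do not support that: the inputs are assumed, good adherence gives 0.98 to 0.90, and even the direction depends on frail patients running at lower BIS.

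Nor do the documents contradict themselves on the BIS summary or the bands. Section 7.2 derives the mean for the intention-to-treat summaries, while section 4.3.2 names the median for classification. Its inclusive limits already assign 40 and 45, so the intermediate group can be read as what lies between. Both points need only clearer wording.

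**Conclusion.** The point holds in form and is moderate in consequence: should-fix. That the comparison is as-treated, mislabelled, and without adjustment tied to it follows from the SAP's text and needs no assumption. The size is conditional. Under a null effect and the stated assumptions, the spurious ratio runs from 0.98–0.90 (arms on target) to 0.85–0.64 (arms converging), and lies above 1 if the frailty relation reverses. Matching the hypothesised 0.80 is possible, not expected.

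Two stronger readings should be resisted. The trial's main conclusion is not compromised, because the intention-to-treat test does not use this grouping. And ignoring randomisation is not the whole source of bias: when the arms converge, a set restricted to each patient's own band still gives 0.89 to 0.75.

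**What to change.** - **Per-protocol set (4.3.2).** Define it as patients whose achieved median BIS lies in the band of their randomised arm, analysed as randomised. Adjust for prespecified baseline covariates already collected: age, ASA, Charlson score, cancer, emergency/elective status and surgery type. State that it is supportive only, because it still selects on a post-randomisation variable.
- **Present grouping.** Keep it if wanted, relabelled as-treated and exploratory, with the same adjustment.
- **Clarifications.** State in section 7.2 that the median is derived for classification, and in section 9.1 that the intermediate group is above 40 and below 45.
- **Optional.** A complier-average causal effect estimate, with randomisation as the instrument, would address depth received without conditioning on achieved BIS.

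The cost is SAP wording and a little programming. Section 13 provides for amendment before database lock. The per-protocol set becomes smaller because crossovers are excluded rather than relabelled: by about 3% of classified patients if the arms hold their targets, or 12% if they converge as assumed in step 5 of the working.

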7 STUDY MEDICATION AND CONCOMITANT THERAPY

7.1 Compliance

To evaluate the degree of compliance with randomised BIS target, tabular summaries of achieved BIS values will be presented by randomised group.

The association between achieved target BIS value and all outcomes will be tested using exploratory analyses as outlined below.

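### The exploratory test of achieved BIS against outcome is outlined only as bands from 30 to 55, which omits both extremes of depth and the variation within bands

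*Combined protocol and SAP*

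**What the plan says.** - **Section 7.1 (Compliance)** announces the analysis: "The association between achieved target BIS value and all outcomes will be tested using exploratory analyses as outlined below". What follows must therefore supply the method.
- **Section 4.3.2 (Per-Protocol Population)** gives two bands of median BIS. For the lighter group: "Participants will be allocated to the BIS=50 group if the achieved median BIS is between 45 and 55 inclusive". For the deeper group: "to the BIS=35 group if the achieved median BIS is between 30 and 40 inclusive". It then states: "Participants who are not within these ranges will be excluded from these analyses".
- **Section 9.1 (Additional analyses), first item**, adds one band: "Additional analyses of efficacy endpoints will be undertaken using the PP participant population and including the intermediate BIS group 40 to 45".
- **Section 9.1, third item**, lists the terms for the multivariable models, ending with "achieved MAP and achieved BIS group on the efficacy endpoints". It does not say what the levels of that group variable are.
- **Section 7.2 (Physiological data)** shows that a continuous value will exist: "Mean BIS for each individual patient will then be calculated". Its only stated use is a descriptive mean and standard deviation by randomised group.

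No section defines a level below 30 or above 55, and none specifies a continuous or dose-response model.

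**The concern.** The targets are 35 and 50, and the outer limits of the bands, 30 and 55, lie exactly 5 units beyond them. Once the middle band is restored, a patient who misses target towards the other arm is kept, while a patient who misses outwards by more than 5 units is dropped. An analysis meant to show whether outcome follows depth would thus lose the deepest and the lightest anaesthetics.

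Both ends bear on questions that the plan itself raises. Section 9 suspects hypotension associated with deep anaesthesia as an explanation for earlier mortality differences, and awareness is a listed endpoint. Treating everyone within a band as having the same exposure loses further information. A null exposure-response result could then reflect the truncated range, and a threshold below 30 could not be seen at all.

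**Working it through.** **1. The plan's own figure.** Section 4.2 gives 3250 per group for p1 = 0.10, p2 = 0.08, power 0.80 and alpha 0.049; section 8.1 makes the test two-sided. The formula is n = [z(1-α/2)·√(2p̄q̄) + z(1-β)·√(p1q1 + p2q2)]² / (p1 - p2)². With p̄ = 0.09 this is [1.9685·√0.1638 + 0.8416·√0.1636]² / 0.0004 = 3233 per group. Power at 3250 is 80.2%. The figure reproduces, and N = 2 × 3250 = 6500 is used below. The documents give no calculation for the achieved-BIS analysis.

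**2. Assumptions, because the documents give no spread.** Each arm's per-patient BIS is taken as normal and rounded to whole numbers. Arm centres run from 35/50 (exactly on target) to 39/47 (arms drifting together), with within-arm SD from 2 to 6. Values of exactly 40 and 45, which fall in two bands as written, are placed in the outer bands.

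**3. Patients outside 30 to 55.** Example with centres 35/50 and SD 5: in the deep arm, P(rounded BIS < 30) = Φ((29.5 - 35)/5) = Φ(-1.1) = 0.1357, and 0.1357 × 3250 = 441. By symmetry 441 in the light arm exceed 55. The total is 882 of 6500, or 13.6%.

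**4. Information kept for a linear trend.** Relative information = (share of patients retained × between-band variance of BIS among them) / (total variance of BIS in all patients). A continuous term in all patients scores 100%. In the same example the total variance is ((50 - 35)/2)² + 5² + 1/12 = 81.3, and the three bands keep about 51%. The SE is multiplied by 1/√0.51, or about 1.4.

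| Within-arm SD | Outside 30-55, centres 35/50 | Outside, 39/47 | Three bands keep, 35/50 | Three bands keep, 39/47 | With two tail bands added, 35/50 | Tail bands added, 39/47 |
|---|---|---|---|---|---|---|
| 2 | 19 | 0 | 93% | 88% | 94% | 88% |
| 3 | 217 | 10 | 80% | 83% | 91% | 84% |
| 4 | 550 | 83 | 65% | 75% | 90% | 84% |
| 5 | 882 | 240 | 51% | 65% | 91% | 85% |
| 6 | 1170 | 454 | 40% | 55% | 91% | 87% |

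Centres of 38/48 give about 73%, 61% and 51% at SD 4, 5 and 6, inside these ranges. Without rounding, the three bands keep 78-92% at SD 2-3, 61-75% at SD 4, 48-64% at SD 5 and 37-53% at SD 6.

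**5. Source of the loss.** At SD 5 with centres 35/50, dropping the tails alone leaves 59%, and banding takes this to 51%. With centres 39/47 the steps are 80% and 65%. At SD 2 hardly anyone is dropped, and the loss is nearly all from banding.

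**6. Share held by patients below 30.** As a fraction of the total sum of squares with centres 35/50, this is 13%, 21% and 27% at SD 4, 5 and 6. With centres drifting together it is smaller.

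**The case against.** The exclusion sentence belongs to a two-group per-protocol comparison. Windows of 5 units around each target are an ordinary way to keep patients who achieved the intended contrast, and dropping the rest follows from that purpose. This stands, and the per-protocol comparison need not change. The gap is that sections 7.1 and 9.1 outline no other exposure for the association test.

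A reader might infer that the multivariable models in section 9.1 also drop everyone outside 30 to 55. The text does not settle this. Only the first item there names the per-protocol population, and the levels of the group variable are simply not given. What can be said is that they are unspecified.

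A reader might also infer that patients below 30 hold most of the signal, or that those above 55 hold most of the awareness signal. The documents support neither. Under a linear effect, those below 30 hold about a quarter of the information at most (step 6). A larger share would need a non-linear harm, which was not modelled. Patients in both tails remain in the intention-to-treat awareness analysis and in the safety population.

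The size of the loss depends on a spread that the documents do not give. BIS is titrated to a target, so a per-patient SD of 2-3 is possible, and the loss is then modest. This stands, and the range must be shown whole.

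Finally, greater precision does not remove confounding of achieved BIS by the patient's condition, and section 13 allows additional analyses by addendum. Both are true. They limit the importance of the point, but the promised test still lacks a method that uses the full exposure range.

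**Conclusion.** The point holds as a gap in an exploratory analysis. Read together, sections 4.3.2, 7.1 and 9.1 define achieved BIS for outcome analysis only as three bands covering 30 to 55. The analysis as outlined omits both extremes and the variation within bands, and it cannot show an effect confined to BIS below 30.

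The cost in linear-trend information is about 7-20% at SD 2-3 (0 to about 220 of 6500 patients outside the bands), 25-35% at SD 4, 35-49% at SD 5 and 45-60% at SD 6 (about 450 to 1170 outside). These figures rest on normal distributions, assumed arm centres and a linear effect. If risk were concentrated in the tails, the loss would be larger.

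It would go too far to read this as a flaw in a secondary objective or in the main result. No objective in sections 3.2 to 3.4 asks whether outcome tracks achieved depth, section 7.1 calls the test exploratory, and the primary comparison is by randomised group in the intention-to-treat population.

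**What to change.** Leave the two-group per-protocol comparison as a separate analysis. For the association test in sections 7.1 and 9.1:

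- Enter achieved BIS as a continuous term, for example a restricted cubic spline, in all intention-to-treat patients with a usable BIS recording.
- Adjust for baseline covariates, and label the analysis observational and exploratory.
- State whether the per-patient value is the median (section 4.3.2) or the mean (section 7.2).
- If bands are kept for display or in the multivariable models, list their levels, add below 30 and above 55, and assign values of exactly 40 and 45 to one band each. Adding the two tail bands alone brings the information kept to 84-94% in the scenarios tabulated.

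The cost is SAP wording and a few lines of code, with no new data. Section 13 allows amendment before database lock, and fixing the form in advance avoids choosing cut-points after seeing results. The downsides are that a curve is slightly harder to present than groups, and that the analysis remains non-randomised and open to confounding.
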